10.9.2 Visit 2 (Week 0) = baseline

Eligible patients will return to the clinic no later than 4 weeks (28 days) after completing the Screening Visit. The following assessments and evaluations will be carried out during this study visit:

- Collect quality of life questionnaires:
 - SF-36 health survey score
 - FACIT fatigue score
- Assess disease activity scores:
 - SLEDAI-2K
 - PGA
 - BILAG-2004 index
 - SELENA-SLEDAI flare index

- SLICC/ACR-DI
- 28- Tender & Swollen Joint Counts
- Joint Pain VAS
- CLASI
- Record all AEs
- Record concomitant medication
- Perform complete physical examination, including body temperature and weight
- Measure vital signs – brachial pulse and blood pressure to be taken after 3 minutes of rest in a supine position prior to and 1 hour post study product administration
- Evaluate eligibility
- Randomization by IWRS
- Perform a 12-lead ECG
- Obtain a Chest X-Ray where allowed by local regulation
- Perform urine pregnancy test for female patients of childbearing potential
- Perform urinalysis, including dipstick and microscopic examination
- Obtain blood sample for:
 - Hematology, coagulation (INR, PT, PTT, fibrinogen), biochemistry (complete)
 - Lymphocytes count (Total, CD4+, CD8+)
 - Anti-IFN α binding antibodies
 - Anti-KLH binding antibodies
 - Anti-IFN α neutralizing antibodies
 - Neutralizing Anti-IFN α antibodies towards IFN α subtypes
 - Anti-IFN α and anti-KLH antibody isotyping
 - IFN β cross-neutralization
 - Anti-dsDNA antibodies

- ANA
- Other autoantibodies (anti-Sm, anti-RNP, anti-SSA/Ro, anti-SSB/La, anti-cardiolipin and anti- β_2 -glycoprotein I antibodies)
- Inflammatory markers (C3, C4, CH50)
- IFN gene signature (by Affymetrix)
- Check contraindications
- Administer study product (two syringes)
- Record solicited injection site reactions during one hour following study product administration
- Record solicited systemic AEs during one hour following study product administration
- Provide diary card for daily recording by the patient of solicited AEs (Day 1 to Day 7)

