13.9.6 Analysis of the Exploratory Endpoints

- Clinical response by assessing disease activity using: 28-Tender and Swollen Joint Counts and Joint Pain VAS will be analyzed using a t-test
- Number of SLE flares will be analyzed using frequency table methods
- Time to first SLE flare in patients will be analyzed using life-table methods
- Proportion of patients with an increase or addition in lupus therapy will be analyzed using frequency table methods

- Proportion of treatment failure will be analyzed using frequency table methods. Patients will be considered as treatment failure if they receive more than 5 mg prednisone equivalent/day at any time between Week 24 (Visit 9) and Week 36 (Visit 12) or if their CS dose is increased above the Week 24 level or if any increase of immunosuppressive treatment between Week 12 and Week 36 above CS dose at Week 12 is recorded.
- Changes in the SF-36 score: Physical Component Summary (PCS) and Mental Component Summary (MCS) scores using non-parametric Wilcoxon-test; if one is statistically significant then the individual domain scores will also be analyzed. Also clinically meaningful improvements \geq Minimum Clinically Important Differences (MCID) of 2.5 points for summary and 5.0 points for domain scores will be analyzed
- Quality of life using FACIT fatigue score will be analyzed using a t-test
- Changes in the levels of auto-antibodies (anti-dsDNA, anti-Smith antigen [anti-Sm], anti-RNP, anti-SSA/Ro, anti-SSB/La, anti-cardiolipin, and anti- β 2-glycoprotein I antibodies) will be analyzed using a t-test
- Changes in the levels of biomarkers (C3, C4, CH50) will be analyzed versus baseline
- Anti-IFN α and anti-KLH antibody isotyping
- Anti-Hemagglutinin antibody response: seroconversion (four fold increase in antibody titers post-vaccination) and seroprotection (HIA antibody titers \geq 1:40 post-vaccination)
- Correlation between immunogenicity responses and clinical or biological parameters will be performed on an exploratory basis

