5.2.4.4 Immunogenicity analysis

The following analysis will be performed on the PP population.

5.2.4.4.1 *Anti-IFN α binding antibody titers.*

- The number of patients with a positive antibody response over time (seropositivity) will be analyzed using frequency table methods (Statistical table 14.2.19). The definitions are the followings:
 - Seropositivity: A positive result (seropositivity) is defined when titer was ≥ 400 dil-1 and a negative result when titer is < 400 dil-1.
- Descriptive analysis will be done on Log-transformed dilution titers for anti-IFN α binding antibodies expressed as dilution factors at each time point. (Statistical table 14.2.20)
- Reverse cumulative distribution curves will be generated using anti-IFN α antibody titers (Statistical figure 14.2.2)
- GMT for anti-IFN α binding antibodies will be presented. Results will be expressed with 95% CI (Statistical table 14.2.21).

All corresponding data will be listed in Listing 16.2.6.7.

5.2.4.4.2 *Anti-IFN α antibody neutralizing capacity (NC50).*

- The number of patients with a positive antibody response over time (seropositivity) will be analyzed using frequency table methods (Statistical table 14.2.22). The definitions are the followings:
 - Seropositivity: A positive result (seropositivity) is defined when NC50 was ≥ 200 dil-1 and a negative result when NC50 is < 200 dil-1.
- Descriptive analysis will be done on Log-transformed NC50 for anti-IFN α neutralizing antibodies expressed as dilution factors at each time point (Statistical table 14.2.23)
- Reverse cumulative distribution curves will be generated using NC50 (Statistical figure 14.2.3)
- GMT for anti-IFN α neutralizing antibodies will be presented. Results will be expressed with 95% CI (Statistical table 14.2.24).

All corresponding data will be listed in Listing 16.2.6.8.

5.2.4.4.3 *Anti-KLH binding antibody titers.*

- The number of patients with a positive antibody response over time (seropositivity) will be analyzed using frequency table methods (Statistical table 14.2.25). The definitions are the followings:

Statistical Analysis Plan

Study Name: IFN-K-002

SAP version & date: v4, 18/Jun/2018

- Seropositivity: A positive result (seropositivity) is defined when titer was ≥ 400 dil-1 and a negative result when titer is <400 dil-1.
- Descriptive analysis will be done on Log-transformed dilution titers for anti-KLH binding antibodies expressed as dilution factors at each time (Statistical table 14.2.26)

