Total scores at each visit and change from baseline by treatment group will be presented. The change at Week 36 will be analyzed using a t-test. (Statistical tables 14.2.39.1 to 14.2.39.2)

All FACIT data will be presented in Listing 16.2.6.14.

5.2.4.5.7 **Autoantibodies**

The levels of auto-antibodies (ANA, anti-dsDNA, anti-Smith antigen [anti-Sm], anti-RNP, anti-SSA/Ro, anti-SSB/La, anti-cardiolipin, and anti- β 2-glycoprotein I antibodies) will be described at each visit by treatment group. Change from baseline by treatment group will be presented for quantitative parameters. For anti-dsDNA, the change at Week 36 will be analyzed using a t-test. (Statistical tables 14.2.40.1 to 14.2.40.2). These analyses will be performed on the PP population.

All auto-antibodies data will be listed in Listing 16.2.6.15.

5.2.4.5.8 **Biomarkers**

The biomarkers (C3, C4, CH50) at each visit and change from baseline by treatment group will be presented. (Statistical tables 14.2.41.1 to 14.2.41.2). For C3 the change at Week 36 will be analyzed using a t-test. These analyses will be performed on the PP population.

All biomarkers data will be listed in Listing 16.2.6.16.

5.2.4.5.9 **Anti-IFN α and anti-KLH antibody isotyping**

Descriptive analysis will be performed on Anti-IFN α and anti-KLH antibody isotyping data. (Statistical table 14.2.42)

All corresponding data will be listed in Listing 16.2.6.17.

5.2.4.5.10 **Anti-Hemagglutinin antibody response following influenza vaccination**

Seroconversion (four folds increase in antibody titers post-vaccination) and seroprotection (HIA antibody titers \geq 1:40 post-vaccination) will be presented by treatment group for each visit. In addition, results by visit will be presented according to status of anti-IFN α neutralizing antibodies (positive/negative) at the corresponding visit (Statistical table 14.2.43). These analyses will be performed on the FAS population, only on patients vaccinated with seasonal Flu and with sample at baseline and post-baseline.

Statistical Analysis Plan

Study Name: IFN-K-002

SAP version & date: v4, 18/Jun/2018

All corresponding data will be listed in Listing 16.2.6.18.

5.2.4.5.11 ***Neutralizing Anti-IFN α antibodies towards IFN α subtypes***

Descriptive analysis will be performed on Neutralizing Anti-IFN α antibodies towards IFN α subtypes data. (Statistical table 14.2.44)

All corresponding data will be listed in Listing 16.2.6.19.

5.2.4.5.12 ***Other***

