5.3 Statistical/Analytical issues

5.3.1 Adjustments for Covariates

All models ANCOVA, MMRM, Logistic regression) will be adjusted on the minimization factors used for randomization (Ethnic (see section 9 Derived data) Origin, Age group, Presence or absence of renal involvement according to the BILAG at screening, With or without CS treatment at screening, With or without HCQ treatment at screening, With or without MMF treatment at screening).

In addition, MMRM will be adjusted on the baseline value.

For “Ethnic origin”, the reclassified values (see section 9 Derived data) will be used for primary analysis. The values from the eCRF will be used for sensitivity analysis. In the same way, for “Presence or absence of renal BILAG at screening”, the re-computed renal BILAG score derived in the statistics analysis datasets will

Statistical Analysis Plan

Study Name: IFN-K-002

SAP version & date: v4, 18/Jun/2018

be used for primary analysis. The values from the eCRF will be used as sensitivity analysis. (Statistical tables 14.2.3.1.4 & 14.2.3.2.3)

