5.4 Data handling conventions

5.4.1 Baseline definitions

For IFN gene signature, only Week 0 (visit 2) will be considered as baseline.

For BILAG scores, a baseline value will be defined for each body system. This baseline will be the value at Week 0 (visit 2).

For other efficacy and safety endpoints the last observation prior to the first dose of study treatment administration will be used as the baseline value. This will usually correspond to the measurement performed at Week 0 before first-dose. However, in case of missing value at Week 0, the last available value recorded during screening will be used as baseline value.

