7.5 LLDAS

Analysis for LLDAS, initially not planned in the protocol, will be done.

8 Software documentation

All summaries and statistical analyses will be generated using SAS version 9.4 or higher.

Statistical Analysis Plan

Study Name: IFN-K-002

SAP version & date: v4, 18/Jun/2018

9 Derived data

Derived variable	Derivation algorithm
Change from baseline to visit V (continuous)	
Change from baseline of variable X=X(Visit V)-X(Baseline)
 
 ○ Negative values indicate a decrease in X ○ Positive values indicate an increase in X
Percent change from baseline to visit V (continuous)	
Percent change from baseline of variable X=100 *[X(Visit V)-X(Baseline)]/X(Baseline)
 
 ○ Negative values indicate a decrease in X ○ Positive values indicate an increase in X
Treatment Compliance (continuous)	
The compliance Ci for patient i will be computed according to:
 $C_i = \frac{D_i^t * 100}{D_i^p}$ 
where D_i^p mg is the total amount (mg) of IP prescribed to patient i and D_i^t is the total amount (mg) of IP actually taken by the patient during the study i.e., before the end of study for patient i.

Treatment compliance (categorical) (if relevant)	
Categorial variable with three modalities:
 
 • $C_i < 80\%$ • $80\% \leq C_i < 120\%$ • $C_i \geq 120\%$
Event Duration	$(\text{End Date}) - (\text{Start Date}) + 1$
BILAG score	See BILAG-2004 Index scoring
SLEDAI-2K and SELENA SLEDAI	Sum of the weights
SLICC/ACR	Sum of items
CLASI	Sum of items
FACIT	See FACIT-Fatigue Subscale Scoring Guidelines (Version 4)

Statistical Analysis Plan

Study Name: IFN-K-002

SAP version & date: v4, 18/Jun/2018

Derived variable	Derivation algorithm
SF-36	See SF-36 Health Survey, Manual and Interpretation Guide
Time to event SLE flare	
SLE flare will be identified in BILAG-2004 scoring.
 
SLE flares are predefined as a BILAG A or B score due to items that were new or worse in any of the eight organ system (Isenberg et Al).
 
For patient with a SLE flare: Time to event = Visit date of corresponding BILAG – Date of Week 0 + 1
 
For patient without SLE flare: Time to event = Date of Week 36 (or date of end of study for patients prematurely withdrawn before Week 36) – Date of Week 0 +1

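### The t-test on raw change in anti-dsDNA is valid, but it would lose much of its power if anti-dsDNA levels are right-skewed

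*SAP*

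**What the plan says.** SAP 5.2.4.5.7 (Autoantibodies, per-protocol population) describes all autoantibodies by visit and reserves a between-group test for one of them: "For anti-dsDNA, the change at Week 36 will be analyzed using a t-test". The t-test comes from protocol 13.9.6, whose bullet beginning "Changes in the levels of auto-antibodies (anti-dsDNA, anti-Smith antigen [anti-Sm" ends by naming a t-test for the whole autoantibody panel.

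Three other parts of the SAP settle what that t-test is:

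- **Scale.** Section 9 (Derived data) gives "Change from baseline of variable X=X(Visit V)-X(Baseline", that is, a difference in original units.
- **Covariates.** Section 5.3.1 says "All models ANCOVA, MMRM, Logistic regression) will be adjusted on the minimization factors used for randomization", which does not reach t-tests. Its next sentence, "In addition, MMRM will be adjusted on the baseline value", limits baseline adjustment to the MMRM.
- **Baseline.** Section 5.4.1 says that "the last observation prior to the first dose of study treatment administration will be used as the baseline value". Protocol 10.9.2 lists "Anti-dsDNA antibodies" among the Week 0 samples, so the covariate will be in the database.

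Elsewhere the SAP does use the log scale. In 5.2.4.4 it says "Descriptive analysis will be done on Log-transformed dilution titers for anti-IFN"α binding antibodies, with parallel wording for the neutralising NC50 and for anti-KLH titres, each with geometric mean titres. For the SF-36 summary scores it uses a Wilcoxon test. For anti-dsDNA it names no log, rank-based or baseline-adjusted analysis.

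**The concern.** Anti-dsDNA is a non-negative concentration in IU/mL. Inclusion criterion 5 accepts ANA of at least 1:160 and/or anti-dsDNA of at least 7.0 IU/mL. Patients below 7.0 can therefore enter on ANA alone, next to patients with no upper limit. A range like that is often right-skewed. If it is, a patient who starts very high can move by far more IU/mL than one who starts near the cut-off, even when both change by the same percentage. The mean raw change and its standard error then rest on a handful of patients.

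Anti-dsDNA is the only autoantibody given a formal comparison, and the protocol synopsis cites it as a marker of more active disease. What is at stake is the chance of detecting a real reduction, and an estimate that describes the typical patient.

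**Working it through.** **Plan's own figure.** Neither document states an SD, correlation, effect or power for anti-dsDNA, so there is nothing to reproduce for this endpoint. The planning calculation in SAP 2.3.2 (80 per arm, difference 32.6, SD 68, two-sided 5%) does reproduce: 85.4% against the stated 85%. It belongs to the IFN gene signature.

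**Inputs.**

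- From the SAP: two-sided 5% (5.1.2) and a raw difference (section 9).
- Assumed: n = 72 per arm (0.9 × the 80 evaluable, because the per-protocol set excludes further patients); log-normal levels; log-scale correlation r = 0.8; a 25% geometric reduction (ratio k = 0.75, ln k = −0.288); log-SD s from 0.5 to 1.5.

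**Formulas.** In units of the baseline mean, Var(X) = e^(s²) − 1 and Cov(X,Y) = e^(r·s²) − 1 for a placebo patient.

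- Raw change: effect 1 − k = 0.25. Placebo variance = 2[Var − Cov]. Active variance = (1 + k²)Var − 2k·Cov.
- Log change: SE = s√(2(1 − r))·√(2/n).
- Log ANCOVA: SE = s√(1 − r²)·√(2/n).

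**Worked case, s = 1.2.** Here e^1.44 = 4.221 and e^1.152 = 3.164, so Var = 3.221 and Cov = 2.164.

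- Raw change: variances 2.112 (placebo) and 1.786 (active); SE = √(3.898/72) = 0.233; z = 0.25/0.233 = 1.07; power Φ(1.07 − 1.96) ≈ 19%.
- Log change: SE = 0.1265; z = 2.27; power ≈ 62%.
- Log ANCOVA: SE = 0.120; z = 2.40; power ≈ 67%.

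The normal approximation is rough for the raw scale under this much skew, so simulation is the better guide there (24%). For the two log-scale analyses, formula and simulation agree closely.

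**Simulated power (72 per arm, r = 0.8, 25% reduction), rounded over repeated runs.**

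| log-SD | Raw-change t-test (SAP) | Log-change t-test | Log ANCOVA |
|---|---|---|---|
| 0.5 | 99% | not run | 100% |
| 0.8 | 67% | 92–93% | 95% |
| 1.2 | 24% | 62% | 65% |
| 1.5 | 12% | 46% | 47% |

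**Where the gain comes from.** The step from raw to log change accounts for nearly all of it. Compared within the same run, log ANCOVA exceeds the log-change t-test by about 2 to 4 points. This matches the variance ratio (1 − r²)/(2(1 − r)) = (1 + r)/2, which is 0.90 at r = 0.8, 0.85 at r = 0.7 and 0.75 at r = 0.5.

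**Mechanism.** The tenth of patients with the highest baselines contribute about 56%, 80% and 90% of the summed squared raw change at log-SD 0.8, 1.2 and 1.5.

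**Type I error.** Null runs of the raw-change t-test at 72 per arm gave roughly 3.5 to 4.8%. A wider grid (60 and 80 per arm, r from 0.5 to 0.8, log-SD 0.5 to 1.5) gave 3.0 to 5.2%. There is no inflation; the test becomes somewhat conservative as skew grows.

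**Sensitivity.**

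- With r = 0.6, raw t-test versus log ANCOVA is 42% vs 76% (log-SD 0.8) and 15% vs 42% (log-SD 1.2).
- With 80 per arm, r = 0.7 and a 30% reduction, it is 43% vs 87% at log-SD 1.0.
- With 30% or 50% of patients held at a low floor at both visits (log-SD 1.2), it is 18% vs 49% or 14% vs 38%.

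**The case against.** The simulation draws data from the model that the proposed ANCOVA fits: log-normal levels with one proportional effect. That flatters the alternative. The floor scenario shows that the 65% at log-SD 1.2 is optimistic if many patients start low, although the ordering of the methods does not change. The documents give no distribution for anti-dsDNA, and at log-SD 0.5 almost nothing is lost. The raw mean difference is also a legitimate quantity in its own right. The SAP reports medians and quartiles (5.1.1) and reviews outliers before the analysis (5.4.2), which would partly expose influential values without giving a more robust test. All of this stands, and it limits the point to a conditional loss of power.

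A reader might infer more than the documents support:

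- **That the test is unsound, or that chance imbalance in a few high values would produce a false result.** Type I error is held at or near 5%, and usually below it.
- **That baseline is ignored.** A change score subtracts baseline. Only its use as a covariate is missing, and that is worth little here.
- **That the SAP logs all its other antibody measures.** It does so for three immunogenicity assays, for description and geometric means only. No log transformation is specified for the other autoantibodies or the influenza HIA titres.
- **That C3 has the same problem.** Nothing in the documents or the calculations indicates skew in C3.

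**Conclusion.** The point holds as a minor one. The planned comparison is valid, but it is on a scale that could waste much of the available information. The loss against log ANCOVA is about 1 point at log-SD 0.5, 28 at 0.8 (95 − 67), 41 at 1.2 (65 − 24) and 35 at 1.5 (47 − 12). These figures rest on assumed log-normality, a proportional effect, 72 per arm and r = 0.8. The smaller gain from baseline adjustment on the log scale depends on r and not on how skewed the raw values are.

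Anti-dsDNA is exploratory, analysed on the per-protocol set and outside the two-step primary testing sequence. The primary conclusion is unaffected.

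**What to change.** Before unblinding, replace the anti-dsDNA sentence in SAP 5.2.4.5.7 with an ANCOVA of log anti-dsDNA at Week 36 on treatment, log baseline and the minimisation factors (the covariates that 5.3.1 already requires of the SAP's other models). Report the geometric-mean ratio with its 95% CI. State a fixed substitute for values below the assay limit, and add a Wilcoxon test of the change as a check. List the departure from protocol 13.9.6 in SAP section 7.

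For C3, adding baseline as a covariate is a small optional gain (variance (1 + r)/2 of the change-score variance); no log transformation is proposed.

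The cost is a few lines of SAP text and a program change, with no new data. If the scale is changed only after unblinding, the new analysis should be labelled post hoc, because it could look chosen for its result.

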SLICC/ACR DI		●										●		
28-Tender and Swollen joint counts		●				●			●			●		
Joint Pain VAS		●				●			●			●	●	●

Visit	1	2	3	4	5	6	7	8	9	10	11	12	FU1*	FU2*
Week	max -4	0	1	4	8	12	16	20	24	28	32	36	60 108 204 252	84 132 180 228 276
		Dose 1 240 mcg	Dose 2 240 mcg	Dose 3 240 mcg		Dose 4 120 mcg			Dose 5 120 mcg					
CLASI		●				●			●			●		
SF-36 survey score		●				●			●			●	●	●
FACIT fatigue score		●				●			●			●	●	●
Record prior medication and vaccination	●													
Record concomitant medication		●	●	●	●	●	●	●	●	●	●	●	●	●
Influenza vaccination	As needed from Visit 5 at each influenza season except within 7 days before or after study product administration													
Anti-Influenza antibody response	Should be performed 28 days +/-7 days after each flu vaccination													
Record solicited injection site reactions 1 hour post study product administration ⁸		●	●	●		●			●					
Record solicited systemic AEs 1 hour post study product administration ⁹		●	●	●		●			●					
Provision of diary card for daily recording of solicited AEs by patients ¹⁰		●	●	●		●			●					

Visit	1	2	3	4	5	6	7	8	9	10	11	12	FU1*	FU2*
Week	max -4	0	1	4	8	12	16	20	24	28	32	36	60 108 204 252	84 132 180 228 276
		Dose 1 240 mcg	Dose 2 240 mcg	Dose 3 240 mcg		Dose 4 120 mcg			Dose 5 120 mcg					
Return, checking and transcription of diary card		•	•	•		•			•					
Record all AEs		•	•	•	•	•	•	•	•	•	•	•	•	•

ACR = American College of Rheumatology; ACS = American Cancer Society; AE = Adverse event; ANA = Anti-nuclear antibodies; BILAG = British Isles lupus assessment group; CLASI = Cutaneous lupus erythematosus disease area and severity index; CRP = C-reactive protein; CS = corticosteroids; DNA = Deoxyribonucleic acid; ECG = Electrocardiogram; FACIT = Functional assessment of chronic illness therapy; IFN = Interferon; KLH = Keyhole limpet hemocyanin; PGA = Physician's global assessment; RT qPCR = Reverse transcription quantitative polymerase chain reaction; SELENA = Safety of estrogen in lupus erythematosus national assessment; SF-36 = Short form-36 questionnaire; SLE = Systemic lupus erythematosus; SLEDAI = SLE disease activity index; SLICC = System Lupus International Collaborating Clinics; VAS = Visual analog scale.

¹ Including body temperature, weight and height; height being measured only during screening.

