10.9.5 Visit 5 (Week 8)

Enrolled patients will return to the clinic 8 weeks (+/- 4 days) after completing Visit 2. The following assessments and evaluations will be carried out during this study visit:

- Assess disease activity scores:
 - BILAG-2004 index
- Collect, check and transcribe diary card into eCRF
- Record concomitant medication
- Record all AEs
- Perform complete physical examination, including body temperature and weight
- Measure vital signs – brachial pulse and blood pressure to be taken after 3 minutes of rest in a supine position
- Perform urine pregnancy test for female patients of childbearing potential
- Perform urinalysis, including dipstick and microscopic examination
- Obtain blood sample for:
 - Hematology, coagulation (INR, PT, PTT, fibrinogen), biochemistry (disease-oriented)
 - Anti-IFN α binding antibodies
 - Inflammatory markers (C3, C4, CH50)

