11.4.4 Concomitant Medications/Vaccinations

Any concomitant medication or any vaccination (name, dose, unit, frequency, route of administration, reason for medication, start and end dates) will be recorded at each visit.

At screening, total duration, duration on stable dose, and current dose of CS, HCQ-CQ, MTX, AZA, MMF, Topical agents and NSAIDs will be recorded. Any other pulse CS, potent immunosuppressive drugs such as cyclophosphamide, cyclosporine A, oral tacrolimus, biologics including but not limited to IFN mabs, rituximab and epratuzumab taken in the past, with time since discontinuation will be recorded.

CS Tapering is encouraged along Induction period and is mandatory along maintenance period as described in Table 4. Tapering is also encouraged for MTX, AZA, MMF, topical agents and NSAIDs from maintenance period onwards as described in Table 4.

At each seasonal period, flu vaccination is allowed according to local practice/recommendation in the different geographic area from Visit 5 at any time except within 7 days before and after study product administration to avoid interference in safety assessment. Blood sample is to be performed 28 days +/- 7 days after flu vaccination within planned visits. Name of vaccine, date of vaccination and of blood sample will be recorded in the eCRF.

Study patient and his/her partner have to use effective method of contraception for the duration of the study period (up to week 36) plus 6 months.

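### Influenza seroconversion is measured from a Week 0 titre taken about 8 to 32 weeks before vaccination; the reference should be the last serum before the vaccine

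*SAP*

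**What the plan says.** **Endpoint.** The protocol (13.9.6) plans "seroconversion (four fold increase in antibody titers post-vaccination" and seroprotection, a post-vaccination titre of at least 1:40. SAP 5.2.4.5.10 repeats this: "Seroconversion (four folds increase in antibody titers post-vaccination". Neither document names the titre from which the four-fold rise is counted. The SAP presents results by arm and visit, and by anti-IFN-alpha neutralising status. It limits both measures to the FAS, "only on patients vaccinated with seasonal Flu and with sample at baseline and post-baseline".

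**Baseline.** SAP 4.1.3 lists the anti-hemagglutinin response among the exploratory efficacy endpoints. The general rule of SAP 5.4.1 therefore applies: "the last observation prior to the first dose of study treatment administration will be used as the baseline value". That is usually Week 0, with screening as the fallback. There is no vaccination-specific baseline.

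**Sampling.** Protocol Table 1 gives one instruction for the influenza antibody sample: "Should be performed 28 days +/-7 days after each flu vaccination". Section 11.4.4 agrees: "Blood sample is to be performed 28 days +/- 7 days after flu vaccination within planned visits". The SAP study plan has the same entry as Table 1. The itemised blood lists for screening, Visit 2 and Visit 5 contain no influenza titre.

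**Vaccination.** Table 1 allows it "As needed from Visit 5 at each influenza season except within 7 days before or after study product administration". Visit 5 is at Week 8: "Enrolled patients will return to the clinic 8 weeks (+/- 4 days) after completing Visit 2".

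**The concern.** A fold rise attributed to a vaccine needs a reference titre close to the vaccination. Here the only reference that the SAP defines is fixed by the first study dose, and no vaccination may take place until Week 8. Whatever happens to the titre in between is counted as part of the vaccine response. Natural exposure raises the apparent rise. Decay lowers it, and decay is plausible: exclusion criterion 17 bars only live vaccines before entry, so a patient may enroll soon after an inactivated influenza vaccine with a high Week 0 titre.

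This is the only vaccine-response assessment in the two documents, and response to influenza vaccination is a stated exploratory objective. Misclassified patients weaken what the trial can say about vaccination under IFN-alpha neutralisation. Separately, the baseline-sample condition also governs seroprotection, which needs no baseline.

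**Working it through.** The plan states no figure for this interval, so there is none to reproduce. The inputs are the visit weeks and windows (protocol Table 5), the vaccination rule and the 28 ± 7 day sample (Table 1, 11.4.4), and the Week 36 limit of the SAP (section 1).

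**1. Gap from Week 0 to vaccination**
- Earliest, nominal: 8 × 7 = 56 days (8.0 weeks).
- Earliest, with Visit 5 four days early: 56 − 4 = 52 days (7.4 weeks).
- Latest with a sample at Week 36, nominal: 36 × 7 − 28 = 224 days (32 weeks).
- Latest with windows: 252 + 4 − 21 = 235 days (33.6 weeks).
- The screening fallback can add up to 28 days.

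**2. Gap between the two titres compared**
- Nominal: 56 + 28 = 84 days (12 weeks) up to 252 days (36 weeks).
- Three study doses (Weeks 0, 1 and 4) come before even the earliest vaccination. All five come before a vaccination after Week 24.

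**3. What the gap does to the ratio**

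Apparent rise = (post-vaccination titre ÷ pre-vaccination titre) × (pre-vaccination titre ÷ Week 0 titre). The second factor is drift. The documents give no value for it. Taking 0.5 to 2 as an assumed range (one doubling step either way):

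| True rise | Drift 0.5 | Drift 1 | Drift 2 |
|---|---|---|---|
| 2-fold | 1-fold | 2-fold | 4-fold (wrongly counted) |
| 4-fold | 2-fold (wrongly missed) | 4-fold | 8-fold |
| 8-fold | 4-fold | 8-fold | 16-fold |

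One doubling step can change the classification in either direction.

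**4. Gap with a pre-vaccination reference**

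Protocol 10.9 lists blood for anti-IFN-alpha antibodies at Visits 2, 4, 5, 6, 7, 9, 10 and 12 (Weeks 0, 4, 8, 12, 16, 24, 28 and 36). The longest interval that matters runs from Visit 7 (Week 16) to one week before the Week 24 dose: 23 − 16 = 7 weeks nominally. If both windows fall unfavourably, it is (168 + 4 − 7) − (112 − 4) = 57 days, about 8 weeks. For a vaccination on the day of Visit 5 it is zero.

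**The case against.** **Can the rise be computed at all?** A reader might infer that it cannot, because no pre-vaccination influenza test is scheduled. The documents do not establish that. SAP 5.2.4.5.10 presupposes a baseline sample, Visit 2 draws blood for several antibody assays, and Table 6 refers to a Laboratory Manual for sample types at each visit. Table 6 omits even the post-vaccination assay, so its silence proves little. What is supported is a remote reference.

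**Would the error mislead the comparison?** A reader might also expect a false signal or false reassurance of known direction. Exposure and decay work against each other, and drift common to both randomised arms mainly blurs the contrast. For illustration, suppose that 5–10% of vaccine non-responders in each arm crossed the threshold through exposure alone (an assumption). The observed rate is then r + (1 − r)p, and the arm difference shrinks by the factor 1 − p: a 20-point gap becomes 19 to 18 points. This stands, although equal drift in the two arms is itself an assumption.

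**Is a pre-treatment reference a fault?** Not in itself. Treatment cannot alter a Week 0 titre, whereas a later reference follows at least three doses. This is a real trade-off and a reason to keep the Week 0 result on display.

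**Is the remedy available?** Protocol 11.5.1 permits additional testing in narrower terms than influenza immunity, subject to consent. Nothing confirms that enough residual serum is stored. This also stands, so the fix must be conditional.

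**Is one common analysis set defensible?** It is tidy, and few patients may be lost if Week 0 serum is assayed for everyone. Requiring a baseline still serves no purpose for a post-vaccination threshold.

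**Conclusion.** The point holds in limited form. Following SAP 5.2.4.5.10 with 5.4.1, the four-fold rise is counted from a titre about 8 to 32 weeks before vaccination (52 to 235 days with windows). Patients can be misclassified in both directions. Neither the size nor the net direction of the error can be derived from the documents; the drift table shows sensitivity under an assumed range. The conclusion rests on applying the SAP's general baseline rule to this endpoint, since no other baseline is defined for it.

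The endpoint is exploratory and descriptive, with no hypothesis test. It does not enter the co-primary tests or the definition of a positive study. The change is worth making because it is cheap and the reference is otherwise poorly matched to the question.

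**What to change.** In SAP 5.2.4.5.10:

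1. Define the seroconversion reference as the HIA titre on the last available serum on or before the vaccination date, assayed together with the post-vaccination sample. Make this conditional on residual serum and on the patient's consent covering the test.
2. Keep the Week 0-referenced result as a supplementary display, labelled as such.
3. If no such serum exists, make post-vaccination GMT and seroprotection by arm the main result, and label any Week 0-referenced seroconversion clearly.
4. In either case, analyse seroprotection in all vaccinated FAS patients with a post-vaccination titre, with no baseline-sample requirement. The list of tables in SAP 10.1 appears to mark Table 14.2.43 for the PP set, while the text says FAS; the same edit should settle this.

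The cost is one extra HIA run per vaccinated patient on existing serum, plus the SAP wording. Sample size and the co-primary analyses do not change.
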